5.1.3.2. Treatment Failure Criteria

Subjects who discontinue study agent due to lack of efficacy, an adverse event (AE) of worsening of psoriasis, or who started a protocol-prohibited medication/therapy during the study that could affect their psoriasis are considered as treatment failures.

The particular protocol-prohibited medications/therapies include:

Topical Therapies:

- Any anti-psoriatic topical therapies used for psoriasis (with the exception of topical moisturizers and shampoos containing tar or salicylic acid only)

Phototherapy or Systemic Therapies:

- Any systemic corticosteroid used for psoriatic arthritis or psoriasis with the exception of intra-articular corticosteroids.
- Any other anti-psoriatic systemic therapy or biologic therapy.
- Phototherapy of UVB or PUVA.
- Any other phototherapy for psoriasis.

5.1.3.3. Treatment Failure Rules

A subject who meets one or more treatment failure criteria specified in Section 5.1.3.2 will be considered a treatment failure from that point onward. The baseline values will be used for all directly measured endpoints regardless of the actual measurements. Zero will be assigned to improvement and percent improvement, and non-responder status will be assigned to binary response variables.

Treatment failure is assumed to have occurred at the earlier of the following dates:

- Date of discontinuation (DC) of study treatment due to lack of efficacy or
- Date of discontinuation of study agent due to an AE of worsening of psoriasis or
- Start date of a protocol-prohibited medication/therapy during the study that could improve psoriasis

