 - Has received phototherapy or any systemic medications/treatments that could affect psoriasis or IGA evaluations (including, but not limited to, oral or injectable corticosteroids, retinoids, 1,25-dihydroxy vitamin D3 and analogues, psoralens, sulfasalazine, hydroxyurea, fumaric acid derivatives, herbal treatments, or traditional Taiwanese, Korean, or Chinese medicines) within 4 weeks of the first administration of study intervention.

- Has used topical medications/treatments that could affect psoriasis or IGA evaluations (including, but not limited to, corticosteroids, anthralin, calcipotriene, topical vitamin D derivatives, retinoids, tazarotene, methoxsalen, trimethylpsoralens, pimecrolimus, tacrolimus, or topical traditional Taiwanese, Korean, or Chinese medicines) within 2 weeks of the first administration of study intervention.
- Is currently receiving lithium, antimalarials, or intramuscular (IM) gold, or has received lithium, antimalarials, or IM gold within 4 weeks of the first administration of study intervention.
- Has received an experimental antibody or biologic therapy within the previous 6 months, or received any other experimental therapy or new investigational agent (topical or systemic) within 30 days or 5 half-lives (whichever is longer) of any study intervention administration or is currently enrolled in another study using an investigational agent or procedure.
- who did not complete the specified exposure to study agent as outline below
 - Subject randomized to guselkumab at Week 0 but did not receive all scheduled guselkumab administrations (ie, Week 0, Week 4, and Week 12), or received one or more extra guselkumab administrations.
 - Subject randomized to etanercept at Week 0 but missed two or more scheduled etanercept administrations (weekly dose through Week 15), or received one or more extra etanercept administrations.

Subjects who discontinued the study agent due to unsatisfactory therapeutic effect or an adverse event (AE) of worsening of psoriasis, or subjects who started prohibited medications and continued receiving study agents prior to Week 16 will be included in the per protocol analysis and the treatment failure rules specified in Section 5.1.3.3 will apply. Subjects who used rescue medication will also be included in the per protocol analysis and the rescue treatment rules specified in section 5.1.3.5 will apply.

Subjects who were excluded from the per protocol analyses will be summarized.

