5.1.3.5. Rescue Treatment Rules

Subjects who use a low to high potency topical steroid starting at Week 8 or Week 12 as a result of being eligible for rescue treatment will be considered as nonresponders for binary endpoints and zero (no change from baseline) will be assigned to continuous outcomes from that point onward through Week 16. The analysis at and after Week 20 will use the observed data without imputation. Treatment failure rules will be applied if subjects continue to use or initiate treatment of a low to high potency topical steroid after Week 20.

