5.1.3.6. Missing Data Imputation

After the treatment failures and rescue treatment rules are applied, the remaining missing data will be handled as follows for all of the efficacy analyses including the analyses at key visits (eg Week 16) and over time through Week 52:

- Non-responder imputation will be applied for binary efficacy endpoints.
- No imputation will be performed for missing post baseline continuous values. The statistical model (ie, MMRM) will adjust for missing data.

For the analyses related to the time to event endpoints during the withdrawal and retreatment period, missing PASI score after the Week 16 visit will not be imputed and the value will remain as missing after applying treatment failure rules.

For the efficacy analyses that evaluate the efficacy of retreatment or initiation of guselkumab, after the treatment failure rules are applied, no imputation will be performed for missing data following the retreatment or initiation of guselkumab.

For the efficacy analyses through LTE period, no treatment failures and no missing data imputation will be performed, and the analyses will be based on observed data.

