 - After retreatment with guselkumab: To evaluate the efficacy of retreatment with guselkumab, efficacy data at and after retreatment (ie, at the time of retreatment, 4 weeks after retreatment, 8 weeks after retreatment) will be summarized for subjects who were randomized to guselkumab at Week 0, were withdrawn from study agent

- at Week 16, experienced a loss of 50% of the Week 16 PASI improvement, and were retreated with guselkumab.
- For subjects who were randomized to placebo at Week 0, and were PASI 90 responders at Week 16, efficacy data will be listed after Week 16.
 - Efficacy of PASI 90 non-responders at Week 16
 - Efficacy analyses for those subjects who were PASI 90 non-responders at Week 16 will be performed for the following treatment groups.
 - ◆ **Placebo → Guselkumab:** Subjects who were randomized to placebo at Week 0, were PASI 90 non-responders at Week 16 and crossed over to guselkumab at Week 16.
 - ◆ **Guselkumab:** Subjects who were randomized to guselkumab at Week 0, were PASI 90 non-responders at Week 16 and continued to receive guselkumab at Week 16.
 - Efficacy of etanercept cross over subjects
 - ◆ **Etanercept → Guselkumab:** To evaluate the efficacy of guselkumab in subjects previously treated with etanercept, efficacy analyses will be performed from Week 20 through Week 52 for subjects who were randomized to etanercept at Week 0, and crossed over to guselkumab at Week 20.

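### In the Part 1 switch and retreatment analyses through Week 52, a treatment failure that arose before guselkumab is carried forward and scored as non-response to guselkumab

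*SAP*

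**What the plan says.** SAP 5.1.3.2 gives three failure criteria: stopping study agent for lack of efficacy, stopping it for an adverse event of worsening psoriasis, and starting a prohibited therapy that could affect psoriasis. SAP 5.1.3.3 sets the duration: "A subject who meets one or more treatment failure criteria specified in Section 5.1.3.2 will be considered a treatment failure from that point onward". It sets the values too: "The baseline values will be used for all directly measured endpoints regardless of the actual measurements", and "non-responder status will be assigned to binary response variables".

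For the analyses of retreatment with, or initiation of, guselkumab, SAP 5.1.3.6 states that "after the treatment failure rules are applied, no imputation will be performed for missing data following the retreatment or initiation of guselkumab". Only missing-data imputation is switched off; the failure rules stay on. SAP 5.5.3 applies Section 5.1.3 to every Part 1 analysis of IGA, PASI, CDLQI, FDLQI and BSA.

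SAP 5.5.2.1 defines the three analyses concerned: placebo participants who "were PASI 90 non-responders at Week 16 and crossed over to guselkumab at Week 16"; etanercept participants who start guselkumab at Week 20; and Week 16 PASI 90 responders on guselkumab who were withdrawn, lost half of their improvement and were retreated.

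Two neighbouring rules do have an end. After rescue treatment, SAP 5.1.3.5 says: "The analysis at and after Week 20 will use the observed data without imputation". For the LTE, SAP 5.1.3.6 drops the failure rules altogether.

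**The concern.** A failure dated before the first guselkumab dose of a period is not an outcome of that dose. Yet the participant is fixed as a non-responder, with baseline scores, at every later visit through Week 52. There are three routes:

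- A placebo participant uses a prohibited topical at Week 10, stays on study treatment and starts guselkumab at Week 16.
- An etanercept participant does the same and starts guselkumab at Week 20.
- A withdrawn responder uses a topical during a flare off drug and is then retreated. The score at retreatment is also replaced by the baseline score, so improvement after retreatment is held at zero.

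The efficacy of retreatment is a stated secondary objective, and SAP 5.5.2.1 says that the etanercept crossover analysis is there to evaluate guselkumab after etanercept. The rule pulls both estimates down for reasons unrelated to guselkumab. The composite rationale in SAP 5.2.2 is written for guselkumab against placebo at Week 16; it does not cover a later treatment period.

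**Working it through.** **Step 1: does anything end the status?** The duration in SAP 5.1.3.3 has no stop date. SAP 5.1.3.6 and 5.5.3 carry the rule into the affected analyses. None of these sections, nor SAP 5.5.2.1, resets it at Week 16, at Week 20 or at retreatment. By contrast, the safety summaries in SAP 7 count, for the crossover groups, only events on or after the first guselkumab administration.

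**Step 2: who can be affected?** Two of the three criteria are discontinuation of study agent and normally mean no later guselkumab. The third can leave a participant on treatment: Protocol 6.5 and 7.1 require discontinuation after a prohibited therapy unless the medical monitor agrees otherwise. Withdrawn responders are exposed because Protocol 6.5.1 bars starting rescue steroids at or after Week 16 and 6.5.2 bars other psoriasis topicals. One point is open: Protocol 4.1 offers etanercept participants guselkumab at Week 20 irrespective of PASI response, without saying whether this includes someone who stopped etanercept early for lack of efficacy. If it does, that criterion carries over as well.

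**Step 3: group sizes.**

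- Placebo to guselkumab: 25 randomised. With the adult placebo PASI 90 rates of 2.4% to 2.9% (Protocol 2.2.1), non-responders number 25 × (1 − 0.029) = 24.3 to 25 × (1 − 0.024) = 24.4, so about 24.
- Etanercept to guselkumab: 25 if all switch. Fewer switchers raise the cost per case (with 20, 1/20 = 5 points).
- Retreated: 40 × 0.70 = 28 withdrawn responders at the lower adult PASI 90 rate. The documents do not give the number retreated; 10 to 28 is an assumption.

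The plan gives no figure for the failure rule itself. Its power figures for these arm sizes do reproduce with an exact unstratified Fisher test: 81.0%, 84.9% and 92.4% for etanercept (stated 81%, 85%, 92%), and 99.3% or more for guselkumab (stated >99%). They concern Week 16 and are not changed by this point.

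**Step 4: size.** Let n be the group size, k the number of carried-over failures and p the true response rate, taken as the same for carried-over and other participants. The reported rate is p(n − k)/n. The expected loss is pk/n, and the maximum loss is k/n, reached if every carried-over participant would have responded. The range 65% to 85% for p is the sample-size assumption for IGA 0/1 and PASI 75 (SAP 1.4), borrowed here for the later periods.

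| Analysis | n | Maximum loss, k = 1 | Expected loss, k = 1 (p = 65% to 85%) | Expected loss, k = 3 |
|---|---|---|---|---|
| Placebo → Guselkumab | 24 | 4.2 | 2.7 to 3.5 | 8.1 to 10.6 |
| Etanercept → Guselkumab | 25 | 4.0 | 2.6 to 3.4 | 7.8 to 10.2 |
| Retreated | 28 | 3.6 | 2.3 to 3.0 | 7.0 to 9.1 |
| Retreated | 14 | 7.1 | 4.6 to 6.1 | 13.9 to 18.2 |
| Retreated | 10 | 10.0 | 6.5 to 8.5 | 19.5 to 25.5 |

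Losses are in percentage points. The values of k are illustrative; the documents give none.

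**The case against.** The route is narrow. It needs a prohibited therapy, an agreed exception and then a switch or retreatment. The period after Week 16 is uncontrolled and its outputs are summaries, so no test is affected, and the error runs against guselkumab. SAP 4.2 lists everyone who met a failure criterion, with the reason, so the cases would be visible. The contrast with the rescue rule proves little: rescue use is permitted and must end by Week 20, whereas prohibited therapy has no such end date, and treating the two differently may be deliberate. A plain reset could also credit guselkumab with the effect of a systemic, biologic or phototherapy stopped shortly before. All of this stands, and it limits both the weight of the point and the form of the remedy. What it does not supply is a reason to count an earlier failure as an outcome of later guselkumab: these summaries estimate response, and a downward error there protects no claim.

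A reader might infer that a retreated participant can never be shown to have regained response. The documents do not support that. The LTE analyses use observed data, and SAP 5.5.2.3 plans summaries at Week 60 and Week 84 in withdrawn and retreated guselkumab participants. These cover only participants who enter the LTE, so they soften the problem without removing it.

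A reader might also take the per-protocol text, "subjects who started prohibited medications and continued receiving study agents prior to Week 16 will be included in the per protocol analysis", as a sign that the SAP expects such participants to carry on through a switch. It settles only who stays in the per-protocol set for the co-primary analyses and says nothing about later periods.

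**Conclusion.** The point holds for three descriptive Part 1 analyses through Week 52: after placebo, after etanercept and after retreatment. In these, a failure that arose on the earlier treatment or off drug is attributed to guselkumab.

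Per case, the loss is at most about 4 points after a switch and at most about 4 to 10 points after retreatment. The expected loss is about 2 to 8.5 points across the three analyses. These figures assume that all etanercept participants switch, that 10 to 28 participants are retreated, and that response is 65% to 85% whether or not a failure is carried over. The number of cases is unknown and probably small, but in groups of this size a single case shows.

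It would go too far to read this as a bias in the trial's main results. The co-primary and major secondary tests stop at Week 16, before any switch; Part 2 has no switch; and the LTE does not use the rule.

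**What to change.** Add to SAP 5.1.3.3, for the Placebo → Guselkumab, Etanercept → Guselkumab and after-retreatment analyses only, that a failure counts if:

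1. its criterion is met on or after the first guselkumab dose of that period; or
2. the prohibited therapy was still in use at that dose; or
3. the prohibited therapy was stopped before that dose, but within the protocol's exclusion window for its class. Failure status then lasts until that window has passed.

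The windows already stand in Protocol 5.2 and would be used for analysis only: 2 weeks for topicals (criterion 17), 4 weeks for immunosuppressants, other systemics and phototherapy (15 and 16), 3 months for anti-TNF agents (11), 6 months for agents against IL-12/23, IL-17 or IL-23 (13), and 12 months for the agents in criterion 14. That last window runs from screening in the protocol and would run to the guselkumab dose here.

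Keep the current rule for the Week 16 endpoints and the after-withdrawal analyses, and report the current version of the three analyses as supportive. In the same edit, align SAP 5.1.3.2 with 5.1.3.5, since the list of prohibited topicals does not exempt permitted rescue steroids.

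The cost is one paragraph and one more derivation by period, with no change to conduct, alpha or the Week 16 results. Some residual effect of the earlier therapy may remain after its window, so the affected participants should be listed with the therapy and its dates.

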5.1.3.4. Rescue Treatment

In Part 1 of the study, participants with a PASI score increase of $\geq 50\%$ from their baseline PASI score at Week 8 or Week 12 will be allowed to use a topical steroid as rescue treatment up until Week 16, with the exception of ultra-high potency topical steroids (eg, clobetasol propionate, halobetasol propionate) which are not allowed at any time. It is recommended that participants use no more than 60 grams of topical steroids per week. In addition, participants should be managed using the lowest possible potency and frequency of rescue topical steroid. Participants must discontinue the use of rescue topical steroids by Week 20.

5.1.3.5. Rescue Treatment Rules

Subjects who use a low to high potency topical steroid starting at Week 8 or Week 12 as a result of being eligible for rescue treatment will be considered as nonresponders for binary endpoints and zero (no change from baseline) will be assigned to continuous outcomes from that point onward through Week 16. The analysis at and after Week 20 will use the observed data without imputation. Treatment failure rules will be applied if subjects continue to use or initiate treatment of a low to high potency topical steroid after Week 20.

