At baseline in Part 1, approximately 40 participants (30 in Part 1a and 10 in Part 1b) will be randomized to guselkumab, and approximately 25 participants (15 in Part 1a and 10 in Part 1b) will be randomized to placebo.

As shown in [Table 1](#), with the conservative assumptions of response rates of 65% in the guselkumab treatment group and 13% in the placebo group, the proposed 40 participants in the guselkumab group and 25 in the placebo group provide at least 99% power to detect a significant difference in the proportion of IGA responders (0 or 1) and PASI 75 responders at Week 16 separately between the guselkumab and placebo treatment groups at a 2-sided significance level of 0.05. These sample sizes are also chosen to ensure sufficient power for major secondary endpoints.

Table 1: Power to Detect a Treatment Effect for Guselkumab Based on Different Assumptions of Response Rates

Endpoint		Power
IGA Score of 0 or 1/PASI 75 at Week 16		
Placebo (n=25)	Guselkumab (n=40)	
13%	65%	>99%
13%	70%	>99%
13%	75%	>99%
13%	85%	>99%

IGA=Investigator's Global Assessment; PASI=Psoriasis Area and Severity Index

Assumptions for Etanercept Response Rates

The PGA responder (0 or 1) rate in the etanercept group of the etanercept pediatric plaque psoriasis study was 53% and the PASI 75 rate was 57%. Therefore, a range of response rates from 53% to 60% for both IGA 0/1 and PASI 75 in the etanercept active comparator treatment group is utilized for the proposed pediatric study.

Power for Etanercept and Placebo Comparisons

With approximately 25 participants (15 in Part 1a and 10 in Part 1b) randomized to receive etanercept, and approximately 25 participants (15 in Part 1a and 10 in Part 1b) in the placebo group, there will be at least 81% power to detect a significant difference in the proportion of IGA responders (0 or 1) and PASI 75 responders at Week 16 separately between etanercept and placebo treatment groups at a 2-sided significance level of 0.05 ([Table 2](#)).

Table 2: Power to Detect a Treatment Effect for Etanercept Based on Different Assumptions of Response Rates

	Endpoint		Power
	IGA Score of 0 or 1/PASI 75 at Week 16		
Placebo (n=25)		Etanercept (n=25)	
13%		53%	81%
13%		55%	85%
13%		60%	92%

IGA=Investigator's Global Assessment; PASI=Psoriasis Area and Severity Index

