5. EFFICACY

Unless otherwise stated, efficacy data summaries will be provided for the full analysis set for each part. The Fisher's exact test, stratified by age group and region, will be used to compare the proportion of subjects responding to treatment if appropriate. Continuous response parameters (i.e. change from baseline in CDLQI) will be compared using Mixed Model Repeat Measurement (MMRM) analysis with factors of treatment, region, age group, baseline, visit, baseline by visit and treatment by visit; or an analysis of covariance (ANCOVA) model, adjusting for baseline value, age group, and region. If the normality assumption is violated, non-parametric methods will be used as appropriate. All statistical testing will be performed at a 2-sided significance level of 0.05.

Descriptive statistics, such as mean, median, standard deviation, minimum and maximum, interquartile range for continuous variables, and counts and percentages for categorical variables will be used to summarize the data. Life table estimates will be provided for the time to event variables. Graphical data displays and subject listings may also be used to summarize the data.

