5.2.2. Primary Estimand

The composite estimand assesses the treatment effects not only based on the variable measurements, but also based on intercurrent event defined in TF criteria and rescue treatment criteria. If a subject had to use rescue medication or meet TF criteria, the subject will be a non-responder for co-primary endpoints. This estimand acknowledges that subjects meeting the TF criteria or using rescue treatment have an unfavorable outcome.

Population: subjects with chronic plaque psoriasis who are randomized to guselkumab or placebo in Part 1 of the study.

Variable: the endpoint is defined as proportion of subjects who achieve an IGA score of cleared (0) or minimal (1) at Week 16 or the proportion of subjects who achieve a PASI 75 response at Week 16. Non-responder status is assigned after meet TF or rescue treatment criteria.

Intercurrent Events: the intercurrent event is captured through the variable definition.

Population-level summary: difference in response proportions between guselkumab group and placebo group.

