5.5.2.1.2. Analyses Related to PASI

5.5.2.1.2.1. Through Week 16

- The proportion of participants who achieve a PASI 50 response at Week 16 will be compared between the guselkumab group and the placebo group using Fisher's exact test stratified by region and age. The differences in proportions with exact 95% confidence intervals will be presented.
- The percent improvement from baseline in PASI at Week 16 will be compared between the guselkumab group and the placebo group using a using Wilcoxon rank-sum test.
- The percent improvement from baseline in PASI will be summarized over time through Week 16 by treatment group.
- The proportion of PASI responses (PASI 50, 75, 90, and 100) will be summarized over time through Week 16 by treatment group. Line plots will be provided displaying proportions and exact 95% CIs of PASI 100 responders and PASI 90 responders through Week 16.
- The proportion of PASI responses (PASI 50, 75, 90, and 100) will be summarized over time through Week 16 by treatment group using observed data after applying treatment failure rules and rescue treatment rules.
- The proportion of subjects who achieve 100% improvement, $\geq 90\%$, $\geq 75\%$, or $\geq 50\%$ improvement from baseline in PASI component (induration, erythema, and scaling) and region component (head, trunk, upper extremities, and lower extremities) will be summarized at Week 16 by treatment group.

5.5.2.1.2.2. From Week 16 through Week 52

PASI 90 responders at Week 16 (after withdrawal of guselkumab)

- The time to loss of PASI 90 response after withdrawal will be summarized for participants randomized to the guselkumab group who were PASI 90 responders at Week 16. The percent of subjects who maintained a PASI 90 response from Week 20 through Week 52 will be estimated from life-table methodology and a survival curve (probability that participants maintain PASI 90 response after withdrawn) will be presented.

- The duration of PASI 90 response will be summarized using life-table methodology for participants randomized to the guselkumab group who were PASI 90 responders at Week 16. The estimated number of weeks at which 90%, 75%, 50% and 25% of subjects maintained a PASI 90 response will be provided.

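### SAP 5.1.3.5 scores rescued participants as zero change in PASI although rescue requires a rise of at least 50%, which flatters mean PASI improvement unless the worsening has reversed by Week 16

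*SAP*

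**What the plan says.** In Part 1, only participants with a PASI increase of at least 50% "from their baseline PASI score at Week 8 or Week 12 will be allowed to use a topical steroid as rescue treatment" (SAP 5.1.3.4; the same rule is in Protocol 6.5.1). Those who then use a low to high potency steroid become nonresponders on binary endpoints, and "zero (no change from baseline) will be assigned to continuous outcomes from that point onward through Week 16" (SAP 5.1.3.5). SAP 5.5.3 extends the data handling rules of 5.1.3 to all PASI analyses in Part 1.

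The treatment failure rule (SAP 5.1.3.3) has the same form: "Zero will be assigned to improvement and percent improvement", whatever was actually measured.

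Among the other secondary analyses, "The percent improvement from baseline in PASI at Week 16 will be compared between the guselkumab group and the placebo group" by a Wilcoxon rank-sum test, and percent improvement is summarized over time by arm through Week 16 (SAP 5.5.2.1.2.1). These p-values are nominal. A participant with neither rescue nor treatment failure keeps the measured value, and missing continuous values are not imputed (SAP 5.1.3.6).

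**The concern.** Zero change penalises someone who had improved. The rescue gate selects the opposite group: everyone who qualifies has a PASI at least half as high again as at baseline. Recording them as unchanged puts them above an unrescued participant who is slightly worse than baseline. Read literally, the rule is triggered by use of the steroid, so two participants measured at -50% can score 0 and -50% according to whether they used it.

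At stake are the mean PASI improvement at Week 16 and the PASI course up to it. No planned analysis of PASI percent improvement drops the rescue rule. The one supplementary analysis without it is for CDLQI (SAP 5.3.5, Table 4). The observed-data PASI summaries in SAP 5.5.2.1.2.1 are of response proportions and still apply both rules.

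**Working it through.** **Inputs.** Rescue threshold: PASI at least 1.5 times baseline (SAP 5.1.3.4). Assigned value: 0 (SAP 5.1.3.5). Arm sizes: 40 guselkumab, 25 placebo (SAP 1.4). Rescue rate: not given.

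**The plan's own figures.** The documents give no number for the rescue rule. Their power figures do reproduce, which confirms the arm sizes. With "conservative assumptions of response rates of 65% in the guselkumab treatment group and 13% in the placebo group", SAP 1.4 says "the proposed 40 participants in the guselkumab group and 25 in the placebo group provide at least 99% power". Exact power of an unstratified two-sided Fisher test at 0.05 is 99.3%, 99.8%, 99.97% and above 99.9% at 65%, 70%, 75% and 85%. For etanercept it is 81.0%, 84.9% and 92.4%, against the stated 81%, 85% and 92%. None of this depends on the scoring of continuous outcomes.

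**Score at rescue.** Percent improvement = 100 x (baseline - PASI) / baseline. At the threshold PASI = 1.5 x baseline, for example 12 to 18, 20 to 30 or 48 to 72, so improvement = -50%. The assigned 0 is better by 0 - (-50) = 50 points, and by more if the rise was larger.

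**When zero stops being favourable.** The Week 16 measurement equals zero change when PASI is back at baseline. From the threshold this is a fall of (1.5 - 1.0) / 1.5 = one third. With a smaller fall, zero is better than the Week 16 measurement; with a larger one, it is worse.

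**Effect on an arm mean if -50% persists to Week 16.** Shift per rescue is at least 50/n, assuming every participant in the arm has a value:
- placebo: 50/25 = 2.0 points
- guselkumab: 50/40 = 1.25 points

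For k rescues in placebo the shift is at least 2k points. Taking k from 0 to 5 as an assumed range, that is at least 0 to 10 points.

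**Effect on the guselkumab-placebo Wilcoxon test.** The statistic counts pairs in which the guselkumab value exceeds the placebo value. Moving a placebo participant from -50 or below up to 0 alters only pairs whose guselkumab value lies between the two scores. SAP 1.4 assumes that 65% to 85% of the guselkumab arm reaches PASI 75, so few can lie there.

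An illustration with assumed distributions that are not in the documents: placebo mean 10 and SD 35, guselkumab mean 85 and SD 20, two placebo rescues measured uniformly from -50 to -90.
- The placebo mean rises by 2 x 70 / 25 = 5.6 points.
- The mean rank of the two rescued participants among 65 goes from 1.5 to about 10.4, a gain in rank sum of 2 x 8.93 = 17.9.
- They pass about 8.93 unrescued placebo participants, each of whom drops two ranks, a loss of 17.9.
- The net change in the placebo rank sum is zero. A guselkumab value below 0 has probability of about 0.00001 (z = -85/20 = -4.25).

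**The case against.** The strongest reply is that little inferential weight rests on this rule, and most of that reply stands.

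- A reader might infer that the Wilcoxon comparison is distorted because rescued participants outrank others who worsened less. For placebo rescues the others are almost all in the same arm, so the rank sum hardly moves. Only a rescue on active treatment could move it materially, and no rate is given for that.
- A reader might take the shift of up to 10 points as the error at Week 16. It is measured against the qualifying Week 8 or Week 12 value and uses an assumed number of rescues. Steroid use and further study treatment come in between.
- A reader might see a contradiction with SAP 5.2.2, which says that "subjects meeting the TF criteria or using rescue treatment have an unfavorable outcome". That sentence belongs to the estimand for the binary co-primary endpoints, where nonresponse is the worst category. No estimand is defined for PASI percent improvement, and for CDLQI the SAP deliberately takes zero as the composite value (5.3.2.2.1).
- A reader might extend the argument to all treatment failures. A failure need not be worse than baseline: an adverse event of worsening psoriasis can follow partial improvement, and failures for lack of efficacy or prohibited therapy can also have improved. For them zero is a penalty.
- A reader might conclude that worsening on active treatment vanishes from the report. It does not: rescue users and treatment failures are listed (SAP 4.2), so are adverse events of psoriasis (SAP 7.1), and rescued participants count as nonresponders through Week 16.
- The text does not settle whether the qualifying visit's own value is replaced or only later ones.

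What the reply does not answer is that, for this outcome, a documented rise of at least 50% is recorded as no change and no planned analysis shows otherwise.

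**Conclusion.** The point holds for PASI percent improvement after rescue. The score is at least 50 points better than the qualifying measurement, and better than that of an unrescued participant who worsened slightly and keeps a negative value. Whether it also beats the Week 16 measurement depends on the response after rescue. If the worsening persists, each rescue lifts the arm mean by at least 2.0 points (placebo) or 1.25 points (guselkumab).

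The effect is mainly on mean PASI summaries. Placebo rescues shrink the apparent guselkumab effect; rescues on an active arm flatter that arm. The binary co-primary and binary major secondary endpoints, the sample size and the power are unaffected. CDLQI and BSA also receive zero, but rescue entry is defined on PASI, so the documents do not show that zero is favourable there. This is a cheap improvement to an analysis with a nominal p-value, not a threat to the trial's main conclusion.

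**What to change.** In SAP 5.1.3.5, for PASI percent improvement, assign the worse of zero and the qualifying Week 8 or Week 12 value from rescue through Week 16. State that the observed value at the qualifying visit is kept. Use the same score in means and in ranks.

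In SAP 5.1.3.3, for treatment failures, assign the worse of zero and the last value measured before failure. Someone last seen at +30% still gets 0; someone last seen at -20% gets -20%.

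Keep the current zero rule as a supportive run. Protocol Appendix 2 says that enrolment is closed. If the Week 16 database lock has already taken place, report the revised scoring as a labelled supplementary analysis.

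The cost is SAP wording and a short derivation from data already collected. The downside is a slightly wider spread in the PASI summaries and reliance on a carried-forward value. No change to the clinical rescue rule is proposed.
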